8.1.9. Other Assessments

Asthma control will be assessed at visits (Visits 2, 5, and 7, EW, early discontinuation) using the ACQ-5 questionnaire. These assessments will be conducted only in subjects who reported a diagnosis of asthma at the Screening visit.

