2.5. Sample Size Determination

A total sample size of approximately 100 subjects (approximately 50 per treatment group, randomized in a 1:1 ratio) is estimated to provide approximately 90% power to detect a treatment difference of 12.0 between GB001 and placebo at a 0.050 two-sided level of significance for the primary endpoint of change from baseline to Week 16 in SNOT-22 score, assuming a common standard deviation (SD) of 16.8 and a dropout rate of 15% using a two-sided t-test.

A total sample size of approximately 64 subjects in the CRSwNP stratum (approximately 32 per treatment group, randomized in a 1:1 ratio) is estimated to provide approximately 80% power to detect a treatment difference of 1.3 between GB001 and placebo at a 0.050 two-sided level of significance for the secondary endpoint of change from baseline to Week 16 in NPS, assuming a common SD of 1.7 and a dropout rate of 15% using a two-sided t-test.

Therefore, the total sample size of approximately 100 subjects overall will consist of approximately 64 subjects in the CRSwNP stratum and 36 subjects in the CRSsNP stratum.

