8.3.3.1. Change from Baseline to Week 16 Endpoints

The VAS for rhinosinusitis is used to evaluate the total severity and is only validated in adult CRS to date ([Fokkens, 2007](#)). The subject is asked to indicate on a VAS the answer to the question: “How troublesome are your symptoms of rhinosinusitis?” The VAS ranks from 0 (Not troublesome) to 10 (Worst thinkable troublesome) (as defined in [Protocol Section 10.7](#)). The disease can be divided into Mild, Moderate, and Severe based on total severity VAS score (0 to 10 cm):

- Mild = VAS 0-3
- Moderate = VAS > 3-7
- Severe = VAS > 7-10

Percentage of maxillary sinus volume occupied by disease on CT scan, volume of the air (mL), volume of mucosa (mL), and thickness of lateral wall (mm) will be calculated each for the left and right sides and averaged for analysis, using the non-missing values at each visit.

Change from baseline to Week 16 in VAS score and percentage of maxillary sinus volume occupied by disease on CT scan, volume of the air, volume of mucosa, and thickness of lateral wall will be analyzed using ANCOVA models without MI. The ANCOVA models will be analogous to those described in [Section 8.3.1.3](#), with the baseline value specific to each endpoint included as a covariate. The models will include covariates for treatment group, disease status stratification factor values used for randomization (CRSwNP with comorbid asthma, CRSwNP without comorbid asthma, and CRSsNP), region (United States, Eastern Europe), and baseline value. LS means, SEs, and corresponding 95% CIs for each treatment group, and differences in LS means, SEs, corresponding 95% CIs, and p-values for the GB001 40 mg group versus placebo will be provided.

Actual values and change from baseline values in VAS scores will be descriptively summarized by visit using as observed data.

VAS score, percentage of maxillary sinus volume occupied by disease on CT scan, volume of the air, volume of mucosa, and thickness of lateral wall data will be presented in by-subject data listings.

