8.3.3.5.2. ACQ-5 Score

The ACQ-5 is a five-item questionnaire which has been developed as a measure of the subject's asthma control that can be quickly and easily completed (Juniper, 2005). The response options for each of these questions consists of a zero (no impairment/limitation) to 6 (total impairment/limitation) scale with the total score ranging from 0 to 30. ACQ-5 score is the average of the 5 non-missing items and will be calculated at each visit for each subject. The MCID is 0.5 points. ACQ-5 will be conducted only in subjects who reported a diagnosis of asthma at the Screening visit.

Change from baseline to Week 16 in ACQ-5 score will be analyzed using an ANCOVA model without MI. The ANCOVA model will be analogous to the model described in [Section 8.3.1.3](#),

and will include covariates for treatment group, region (United States, Eastern Europe), and baseline ACQ-5 score. Actual and change from baseline values in ACQ-5 score will be descriptively summarized by visit using as observed data.

ACQ-5 scores will also be presented in a by-subject data listing.

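### VAS and ACQ-5 are measured repeatedly but compared between arms only by observed-case ANCOVA at Week 16, with no imputation and no sensitivity analysis

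*SAP*

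**What the plan says.** **Data collected.** The VAS row of the Schedule of Activities (Protocol 1.3) marks several post-baseline visits. Its columns are misaligned in the text available to me. I read it as baseline and Weeks 4, 8, 12 and 16, plus the early-withdrawal and early-discontinuation visits. SAP 8.3.3.1 confirms that VAS is repeated: "Actual values and change from baseline values in VAS scores will be descriptively summarized by visit using as observed data". For ACQ-5, Protocol 8.1.9 states: "Asthma control will be assessed at visits (Visits 2, 5, and 7, EW, early discontinuation) using the ACQ-5 questionnaire". Visits 2, 5 and 7 are Weeks 0, 8 and 16.

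**Analysis.** SAP 8.3.3.1 assigns "Change from baseline to Week 16 in VAS score and percentage of maxillary sinus volume occupied by disease on CT scan", with the other CT measures, to ANCOVA without MI. SAP 8.3.3.5.2 states: "Change from baseline to Week 16 in ACQ-5 score will be analyzed using an ANCOVA model", again without MI. Table 1 gives neither endpoint a missing-data threshold or a sensitivity analysis.

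**Comparators.** SNOT-22 has an MMRM on all visits through Week 16, with MI added if 10% or more of subjects lack the Week 16 change (SAP 8.3.1). PM nasal congestion, PM TSS and the single diary symptom scores have MMRM without MI (SAP 8.3.2.1.2). Table 1 lists them under Additional, the same tier as ACQ-5. VAS is under Exploratory.

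**The concern.** ANCOVA suits the CT measures that share the VAS sentence, because they have one scheduled post-baseline visit and so no intermediate data to use. VAS and ACQ-5 do have such data, yet the SAP uses it only in by-visit summaries and listings. It gives no reason for treating these two endpoints differently from the diary scores.

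The difference lies in the missing-data assumption. ANCOVA on observed Week 16 values needs missingness to be unrelated to intermediate scores once treatment, baseline score and the other covariates are accounted for. MMRM lets missingness depend on the scores already seen. Dependence is plausible here, since Protocol 7.2 lists lack of efficacy among the reasons for withdrawal.

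VAS may also be missing more often than SNOT-22. For visits missed because of the pandemic, Protocol Appendix 11 includes SNOT-22 in the minimum contact. It names SNOT-22, UPSIT and ACQ-5 as examples for home completion, and VAS appears in neither place.

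At stake is the reading of two low-tier endpoints. If VAS and SNOT-22 disagreed, part of the gap could come from the method and the subjects included, not from the drug.

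**Working it through.** **1. The plan's dropout figure.** SAP 2.5 plans "approximately 50 per treatment group, randomized in a 1:1 ratio", "assuming a common standard deviation (SD) of 16.8 and a dropout rate of 15% using a two-sided t-test". With n = 50 × 0.85 = 42.5 per arm, SE = 16.8 × √(2/42.5) = 3.644, and 12.0/3.644 − 1.960 = 1.333. Power is therefore 90.9% (90.2% with the noncentral t), against the plan's statement that the sample size "is estimated to provide approximately 90% power to detect a treatment difference of 12.0 between GB001 and placebo". The figure reproduces. No power is given for VAS or ACQ-5, so I borrow the 15%: about 100 × 0.15 = 15 subjects with no Week 16 VAS.

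**2. Who is lost.** SAP 3.1 sets target days at week × 7 + 1, splits windows at midpoints (the midpoint goes to the later window), and closes Week 16 at Day 120 for efficacy.
- VAS: Week 12 is Day 85 and Week 16 is Day 113. The midpoint is (85 + 113)/2 = 99, so the window is Day 99 to 120.
- ACQ-5, if windows follow its own schedule: Week 8 is Day 57. The midpoint is (57 + 113)/2 = 85, so the window opens at Day 85.

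An early-withdrawal visit inside the window counts as Week 16. At Day 95, for example, it would count for ACQ-5 on that reading but not for VAS.

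**3. Precision.** Assumptions: correlation ρ from 0.3 to 0.8, compound symmetric (CS) or AR(1), baseline-adjusted, dropout d spread evenly over the intervals. With S the covariance of post-baseline scores given baseline, K the Week 16 visit, and w the share of subjects with each pattern:
- ANCOVA variance ∝ S_KK/(1 − d)
- MMRM variance ∝ the (K,K) element of [Σ w S_obs⁻¹]⁻¹, summed over patterns

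With two visits (ACQ-5) and d = 0.15, 92.5% are observed at Week 8 and 85% at Week 16. The ratio becomes (1/0.85) / [(1 − r²)/0.85 + r²/0.925], where r is the Week 8–16 correlation given baseline. For CS with ρ = 0.5, r = 0.25/0.75 = 1/3, and the ratio is 1.1765/1.1659 = 1.009.

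Ratio of ANCOVA to MMRM variance at 15% missing:

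| | ρ 0.3 | 0.5 | 0.7 | 0.8 |
|---|---|---|---|---|
| VAS, CS | 1.010 | 1.019 | 1.028 | 1.032 |
| VAS, AR(1) | 1.004 | 1.013 | 1.030 | 1.041 |
| ACQ-5, CS | 1.004 | 1.009 | 1.014 | 1.016 |
| ACQ-5, AR(1) | 1.007 | 1.016 | 1.027 | 1.033 |

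The largest ratio, 1.041, widens the confidence interval by a factor of √1.041 = 1.020. At 5% missing the variance loss is about 1% or less.

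**4. Bias.** Large-sample simulation, true effect about −1, missingness depending only on observed scores. Entries are true effect / ANCOVA / MMRM-type likelihood, then the ANCOVA shortfall:

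| | Both arms lose poor scorers | Only placebo does; active loss random |
|---|---|---|
| VAS, ρ 0.5 | −0.995 / −0.982 / −0.996 (1.3%) | −1.010 / −0.911 / −1.009 (9.8%) |
| VAS, ρ 0.7 | −1.018 / −0.996 / −1.021 (2.2%) | −0.991 / −0.912 / −0.989 (8.0%) |
| ACQ-5, ρ 0.5 | −1.001 / −0.985 / −1.000 (1.6%) | −0.994 / −0.919 / −0.993 (7.5%) |
| ACQ-5, ρ 0.7 | −1.006 / −0.990 / −1.004 (1.6%) | −1.006 / −0.934 / −1.004 (7.2%) |

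Missing fractions were 17% to 19% on placebo and 14% to 15% on active. The likelihood analysis stayed within 0.5% of the truth. Here ANCOVA understates the effect, because the placebo subjects who remain look better. If the active arm alone lost its poor scorers, the error would run the other way.

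**The case against.** The strongest reply is that this is a preference about low-tier endpoints. Neither VAS nor ACQ-5 is powered. Every continuous endpoint in the Exploratory tier gets ANCOVA without MI, which is a uniform prespecified convention, and the protocol sets no model for either endpoint, so nothing is contradicted. All of that stands. It does not explain ACQ-5, which shares the Additional tier with diary scores that do get MMRM.

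It can also be said that a like-for-like comparison with SNOT-22 partly exists. Below 10% missing, SNOT-22 has ANCOVA without MI as its sensitivity analysis. At 10% or more its primary analysis is MMRM with MI, so MMRM without MI for VAS would match only a SNOT-22 sensitivity analysis. That stands too. The case for MMRM here is the weaker missing-data assumption, not an exact match to SNOT-22.

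Several stronger readings are tempting but unsupported:
- *The analysis is restricted to completers.* Subjects who stop treatment are encouraged to stay and complete visits (Protocol 7.1), and early-withdrawal values inside the window count.
- *Anyone leaving after Week 12 is lost.* This fails for a VAS early-withdrawal visit from Day 99 to 120, and possibly for ACQ-5 from Day 85.
- *Any link between dropout and symptoms biases the result.* The VAS model adjusts for baseline score, stratum and region, and the ACQ-5 model for baseline score and region. Only dependence on post-baseline scores beyond those covariates matters.
- *The analysed set is healthier.* That is plausible, but nothing in the documents shows it.
- *Earlier scores disappear from the report.* They remain in the by-visit summaries and listings.

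**Conclusion.** The point holds as a minor one. VAS and ACQ-5 are compared by a method that ignores collected intermediate scores and needs a stronger missing-data assumption than the MMRM already specified for similar endpoints, with no sensitivity analysis to show whether it matters.

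The precision cost at 15% missing is small: 0.4% to 4.1% in variance for VAS and 0.4% to 3.3% for ACQ-5. A reader might expect a loss nearer 6%. The calculation reaches 5.7% only for VAS at 20% missing with AR(1) correlation 0.8, which is above the planned dropout. Bias is the better reason to act: about 1% to 2% under a shared dropout mechanism and 7% to 10% if only placebo dropout depends on poor scores. Opposite mechanisms in the two arms gave 16% to 22%, but with 24% to 27% missing on active. That is a stress case, not an expectation.

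All these sizes rest on assumed correlations and dropout patterns, and on the 15% borrowed from the SNOT-22 calculation. ACQ-5 gains less from intermediate data than VAS, having one intermediate visit and an asthma-only subset of unstated size. Nothing here touches the primary or secondary conclusions.

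**What to change.** In SAP Table 1, 8.3.3.1 and 8.3.3.5.2:
- Analyse VAS at all post-baseline visits through Week 16 with the MMRM without MI of SAP 8.3.1.1, using baseline VAS and its interaction with visit.
- Analyse ACQ-5 at Weeks 8 and 16 with the same model form, keeping its own covariates of region and baseline ACQ-5.
- Report the Week 16 contrast for each, and keep the present ANCOVA as a sensitivity analysis.
- Leave the CT measures on ANCOVA.
- State whether analysis windows follow each endpoint's own visit schedule, since this decides which ACQ-5 early-withdrawal values count as Week 16.

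If the sponsor prefers observed-case ANCOVA, one sentence giving the reason would at least make the choice explicit.

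The cost is SAP wording and a few extra model runs. The model and its convergence fallbacks are already specified for the diary scores, and no new data are needed. If the study has already been unblinded, SAP section 1 allows the MMRM to be reported as an additional analysis labelled post hoc.

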8.3.3.2. Change from Baseline to Week 16 Including All Data Endpoints

Additional analyses of change from baseline to Week 16 in SNOT-22 total score, NPS, and Lund-Mackay score will be performed including all data. For these analyses, analysis visit windows will be the same as the primary analysis, except no upper bound will be applied to the Week 16 analysis visit window. The primary analysis approach will depend on the amount of missing data for each endpoint, based on the same criteria for the primary endpoint as described

in [Section 8.3.1](#). The MMRM models for SNOT-22 total score and NPS will be similar to those described in [Sections 8.3.1.1](#) and [8.3.1.2](#), with the baseline score specific to each endpoint included as a covariate. The ANCOVA model for Lund-Mackay score will be analogous to those described in [Sections 8.3.1.3](#) and [8.3.1.4](#), with the baseline score included as a covariate. For the NPS endpoint, the analysis will be conducted within the randomized CRSwNP stratum.

8.3.3.3. Annualized Rate of CRS Exacerbations

The date of onset of a CRS exacerbation will be considered to be the first date of treatment with an antibiotic, an anti-inflammatory drug, or a symptom reliever, the date of Emergency Department visit, or the date of hospitalization, whichever occurs first. The end date of a CRS exacerbation will be considered to be the last date of treatment with an antibiotic, an anti-inflammatory drug, or a symptom reliever, or 6 days after the date of onset (for a total duration of 7 days), whichever is later. Courses of treatment separated by 7 or more days will be counted as separate exacerbations.

The number and proportion of subjects with 0, 1, and ≥ 2 CRS exacerbations and the adjusted annualized rate of CRS exacerbations will be summarized by treatment group. The unadjusted annualized rate of CRS exacerbations will be calculated as the total number of CRS exacerbations divided by the total number of subject-years of follow-up and will also be summarized by treatment group.

The total number of CRS exacerbations will be analyzed using a negative binomial regression model, with the logarithmic transformation of follow-up time as the offset parameter. The follow-up time is defined as the subject's time on study through Day 120. The model will include terms for treatment group, disease status stratification factor values used for randomization (CRSwNP with comorbid asthma, CRSwNP without comorbid asthma, and CRSsNP), and region (United States, Eastern Europe). If the distribution of CRS exacerbation data is underdispersed, or if the negative binomial regression model fails to converge, a Poisson regression model will be used instead of the negative binomial regression model.

The rate ratio for the GB001 40 mg group versus placebo, corresponding 95% CI, and p-value will be provided from the model. The percentage reduction and corresponding 95% CI will also be provided.

Lastly, the subject CRS exacerbation rate will be calculated as the number of CRS exacerbations for each subject divided by the number of years followed in the study for that subject and will be summarized by treatment group.

Analyses of annualized rate of CRS exacerbations may also be presented by various time periods (Baseline through Week 8, Week 8 through Week 16, and Baseline through Week 20 [Follow-up]) in order to elucidate onset and durability of effect over time.

CRS exacerbation data will also be presented in by-subject data listings.

8.3.3.4. Proportion of Subjects with Antibiotic Use Due to Worsening CRS by Week 16

The proportion of subjects with antibiotic use due to worsening of CRS by Week 16 will be analyzed using a logistic regression model to compare the GB001 40 mg group with placebo, using the approach described in [Section 8.3.1.5](#), excluding baseline SNOT-22 total score as a covariate in the model.

8.3.3.5. Other Endpoints

8.3.3.5.1. Nitric Oxide

Nitric oxide will be measured both by oral (FeNO) and nasal (nasal nitric oxide [nNO]) methods. nNO data will be analyzed for the same nostril, either left or right, per subject at all visits. The primary nNO analysis will include subjects with a change from baseline to Week 16 value for a single nostril and subjects with change from baseline to Week 16 values for both nostrils where the nostril with the lower (i.e., worse) value at baseline is used. In the case of ties at baseline, the nostril with the lower (i.e., worse) change from baseline at Week 16 will be selected for summary. A sensitivity nNO analysis will include subjects with a change from baseline to Week 16 value for a single nostril and subjects with change from baseline to Week 16 values for both nostrils where the nostril with the higher (i.e., better) value at baseline is used. In the case of ties at baseline, the nostril with the higher (i.e., better) change from baseline at Week 16 will be selected for summary.

Change from baseline to Week 16 in both FeNO and nNO and percent change from baseline to Week 16 in both FeNO and nNO will be analyzed using ANCOVA models without imputation. LS means, SEs, and corresponding 95% CIs for each treatment group, and differences in LS means, SEs, corresponding 95% CIs, and p-values for the GB001 40 mg group versus placebo will be provided. The models will include covariates for treatment group and baseline FeNO or nNO. Analyses may be conducted using log transformed data in the case of non-normality.

Actual, change from baseline, and percent change from baseline values in FeNO and nNO will be descriptively summarized by visit using as observed data.

Nitric oxide data will also be presented in a by-subject data listing.

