8.2. Efficacy Endpoints

[Table 1](#) provides a summary of the statistical models/methods of primary and sensitivity analyses to be used for the primary, secondary, and select exploratory endpoints. For all efficacy analyses, disease status stratification factor values used for randomization (CRSwNP with comorbid asthma, CRSwNP without comorbid asthma, and CRSsNP) and region (United States, Eastern Europe) will be used as covariates and results will be summarized for the ITT population, unless otherwise stated.

Table 1: Efficacy Endpoints and Analysis Methods

Efficacy Endpoints	Missing Data Threshold ^a	MMRM		ANCOVA		Cox Proportional Hazards	Negative Binomial Regression ^b	Logistic Regression
		without MI	with MI	without MI	with MI			
Primary Change from baseline to Week 16 in SNOT-22 total score	< 10%	P		S				
	≥ 10%	S	P		S			
Secondary								
Change from baseline to Week 16 in Lund-Mackay score	< 10%			P				
	≥ 10%			S	P			
Change from baseline to Week 16 in NPS ^c	< 10%	P		S				
	≥ 10%	S	P		S			
Time to first response (≥ 1 point improvement from baseline) in NPS ^c						P		
Change from baseline to Week 16 in AM NC score	< 10%	P		S				
	≥ 10%	S	P		S			
Change from baseline to Week 16 in AM TSS	< 10%	P		S				
	≥ 10%	S	P		S			
Change from baseline to Week 16 in UPSIT score	< 10%			P				
	≥ 10%			S	P			
Time to first CRS exacerbation						P		
Exploratory								
Change from baseline to Week 16 in VAS score				P				
Annualized rate of CRS exacerbations							P	
Change from baseline to Week 16 in percentage of maxillary sinus volume occupied by disease on CT scan				P				

Efficacy Endpoints	Missing Data Threshold ^a	MMRM		ANCOVA		Cox Proportional Hazards	Negative Binomial Regression ^b	Logistic Regression
		without MI	with MI	without MI	with MI			
Proportion of subjects with antibiotic use due to worsening CRS by Week 16								P
Change from baseline to Week 16 in FeNO and nNO				P				
Percent change from baseline to Week 16 in FeNO and nNO				P				
Additional								
Change from baseline in SNOT-22 total score including all data	< 10%	P						
	≥ 10%		P					
Proportion of subjects with a ≥ 9 point decrease from baseline at Week 16 in SNOT-22 total score								P
Change from baseline in Lund-Mackay score including all data	< 10%			P				
	≥ 10%				P			
Change from baseline in NPS ^c including all data	< 10%	P						
	≥ 10%		P					
Proportion of subjects with a reduction from baseline of ≥ 1 in NPS ^c at Weeks 8 and 16								P

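### The exploratory FeNO and nNO models omit strata and region without a reason, break nostril ties by the Week 16 outcome, and leave the log option without a trigger or definition

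*SAP*

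**What the plan says.** SAP Section 8.3.3.5.1 sets four rules for nitric oxide.

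- **Scale.** Change and percent change are both planned: "percent change from baseline to Week 16 in both FeNO and nNO will be analyzed using ANCOVA models without imputation". Table 1 marks each as a primary-approach ANCOVA under the exploratory endpoints. The section then adds: "Analyses may be conducted using log transformed data in the case of non-normality".
- **Covariates.** "The models will include covariates for treatment group and baseline FeNO or nNO". Neither the disease-status strata nor region is listed.
- **Nostril for nNO.** One nostril per subject is followed at all visits. With two usable nostrils, the primary analysis takes the one with the lower baseline and the sensitivity analysis the one with the higher baseline.
- **Ties at baseline.** In the primary analysis "the nostril with the lower (i.e., worse) change from baseline at Week 16 will be selected for summary". The sensitivity analysis takes the nostril with the higher change.

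Section 8.2 gives the general rule for efficacy models: the disease-status strata used at randomization and "region (United States, Eastern Europe) will be used as covariates and results will be summarized for the ITT population, unless otherwise stated". The VAS and CT-volume models in Section 8.3.3.1 follow it: "The models will include covariates for treatment group, disease status stratification factor values used for randomization", then region and baseline. The ACQ-5 model in Section 8.3.3.5.2 has its own shorter list, "and will include covariates for treatment group, region (United States, Eastern Europe), and baseline ACQ-5 score".

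**The concern.** Each of the three rules leaves something avoidable in the analysis.

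1. Randomization is stratified by country, polyp status and, among polyp subjects, asthma. Leaving those factors out of the model gives up whatever variance they explain. It also leaves the model-based standard error too large, because the stratified design has already balanced the arms on them.
2. A tie rule that looks at Week 16 uses the outcome to decide which outcome is analysed. The primary and sensitivity analyses then differ in opposite directions by construction, so part of any gap between them says nothing about robustness. A tied subject without Week 16 values also has no defined nostril for the by-visit summaries.
3. The log sentence gives no test, threshold, decision-maker or timing. It does not say whether log replaces or supplements the raw analysis, or which quantity is logged. The planned responses are a change and a percent change, and neither has a logarithm when it is zero or negative.

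At stake are the precision and clarity of two exploratory markers for which the SAP plans p-values.

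**Working it through.** **Analysable numbers.** The documents give no power, SD or effect for FeNO or nNO. The only planning figure to reproduce is SNOT-22 (SAP Section 2.5): 50 per arm, difference 12.0, SD 16.8, 15% dropout.

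- Per arm after dropout: 50 × 0.85 = 42.5.
- Noncentrality: 12.0 / (16.8 × √(2/42.5)) = 12.0 / 3.644 = 3.29.
- Two-sided t-test power at 0.05: 90.2%, against approximately 90% stated. It reproduces. I use 42 per arm below.

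**1. Strata and region.** Let R² be the share of residual variance, after baseline, that strata and region explain. The adjusted SE is √(1 − R²) times the unadjusted one. With perfect stratified balance, the unadjusted nominal 5% test has size 2[1 − Φ(1.96/√(1 − R²))]. The R² values are assumed.

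| R² | SE ratio | Unadjusted SE too large by | Equivalent extra subjects | Size of unadjusted test |
|---|---|---|---|---|
| 2% | 0.990 | 1/0.990 − 1 = 1.0% | 2.0% | 4.8% |
| 5% | 0.975 | 2.6% | 5.3% | 4.4% |
| 10% | 0.949 | 5.4% | 11.1% | 3.9% |

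Adjustment uses three more parameters (two for strata, one for region), so residual degrees of freedom go from 84 − 3 = 81 to 78.

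**2. Tie-break.** For two nostril changes with common SD and correlation ρ, the expected lower one lies SD × √((1 − ρ)/π) below the mean, and the expected higher one lies as far above. For a tied subject the shift is 0.47 SD at ρ = 0.3, 0.40 at 0.5, 0.31 at 0.7 and 0.18 at 0.9. The tie frequency is not given, so I take 2-20%.

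- Arm mean at ρ = 0.5: 0.02 × 0.40 = 0.008 SD up to 0.20 × 0.40 = 0.08 SD, downward in the primary analysis and upward in the sensitivity analysis.
- Treatment difference, equal nostril spread in both arms: the shifts cancel.
- Treatment difference, 20% ties and ρ of 0.5 in one arm, 0.8 in the other: 0.20 × (0.399 − 0.252) = 0.029 SD. Simulation (4,000 runs, 42 per arm) also gives 0.029.
- Simulated type I error with 2-20% ties: 0.046-0.057. With no ties it was 0.049-0.055, so the rule has no visible effect.

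**3. Scale.** Simulated ANCOVA with 5,000 runs, 42 per arm, lognormal data and a baseline to Week 16 correlation of 0.7 on the log scale. All of these inputs are assumed.

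| Type I error at log-SD | 0.3 | 0.6 | 0.8 |
|---|---|---|---|
| Log fixed in advance | 0.048 | 0.052 | 0.052 |
| Fixed normality test on residuals decides raw or log | 0.050 | 0.053 | 0.053 |
| Better of raw change and log | 0.059 | 0.071 | 0.073 |
| Best of change, percent change and log | 0.067 | 0.085 | 0.087 |

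With a true effect of −0.25 on the log scale, power for raw change, percent change and log is 0.64, 0.69 and 0.75 at log-SD 0.6, and 0.36, 0.40 and 0.51 at log-SD 0.8. At log-SD 0.3 all three are 0.999.

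**The case against.** **The SAP permits the exception.** Section 8.2 applies its covariates only where nothing else is stated, and Section 8.3.3.5.1 states a different list. A reader might infer that the SAP breaks its own rule; the wording does not support that. What stands is that the exception has no reason. ACQ-5 has a plausible ground for dropping the strata, since it is confined to subjects with asthma, and it still keeps region. Baseline nitric oxide may already absorb stratum differences, so the gain could be near the bottom of the range. The omission errs toward conservatism and creates no false-positive risk.

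**The log option is not a choice between p-values.** A reader might infer that the scale will be picked after seeing which result is better. The text makes log conditional on non-normality, not on significance, change and percent change are planned in advance, and the SAP was finalized before unblinding. The figures of 0.059-0.087 require free picking, which the documents do not describe; a fixed normality rule holds 0.050-0.053. On skewed data the log option helps. The missing trigger and the missing definition remain.

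**The tie rule does not bias the comparison.** A reader might infer a biased treatment effect. The rule applies identically in both arms, so the difference moves by about 0 to 0.03 SD even at 20% ties.

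**The endpoints are minor.** A reader might treat these as the target-pathway markers of a mechanism study. Nitric oxide is named in no listed objective or endpoint, Protocol Section 8.1.8 says only that it may be measured, and Protocol Section 8.6 assigns target engagement and pathway markers to nasal fluid, blood and urine. This stands in full and limits the weight of the point.

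**Conclusion.** The point holds as a free improvement to one exploratory section.

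- **Covariates:** the omission is unexplained and costs about 1-5% in SE if strata and region explain 2-10% of residual variance. That range is assumed. The test is slightly conservative, at about 4.8% down to 3.9% under perfect balance.
- **Tie rule:** it selects on the outcome and pushes arm means in opposite directions in the two nNO analyses, by up to about 0.08 SD each at 20% ties and ρ = 0.5 (both assumed). The treatment difference barely moves.
- **Log option:** it lacks a trigger, a timing and a definition of the logged quantity. Inflated type I error is not shown, because it depends on behaviour the SAP does not describe.

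The primary and secondary analyses are untouched.

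**What to change.** Amend SAP Section 8.3.3.5.1 and the matching Table 1 rows, by a dated addendum before unblinding:

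1. Add the disease-status strata used at randomization and region to the FeNO and nNO ANCOVAs, as in Section 8.3.3.1.
2. Break baseline nostril ties by a rule that ignores Week 16 data, such as a fixed side or the mean of the two tied nostrils, in both nNO analyses. Keep the planned lower-baseline and higher-baseline definitions otherwise. Averaging nostrils for every subject would change the planned measure and is not needed.
3. Fix the log analysis as log(Week 16/baseline) with log baseline as covariate, reported as a ratio of geometric means, and keep raw change and percent change as supportive. SAP Section 3 already analyses values carrying a less-than sign at the stated limit, so such values can be logged.

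The cost is SAP wording and results reported as ratios. No new data are needed.
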